9.6. Data management

Patient information will be abstracted and managed by study sites on eCRFs by a web-based electronic data capture (EDC) tool. All data will be collected and entered directly into the EDC system. All participating sites will have access to the data entered regarding the individual site and its own enrolled patients. All sites will be fully trained on using the online data capture system, including eCRF completion guidelines and help files. Sites will be responsible for entering extracted patient data into a secure EDC database via the eCRF. Investigators and site personnel will be able to access their account with a username and password. All eCRFs should be completed by designated, trained personnel or the study coordinator, as appropriate. In most cases, the eCRF should be reviewed, electronically signed, and dated by the investigator. All changes or corrections to eCRFs are documented in an audit trail and an adequate explanation is required.

A data management plan will be created before data collection begins and will describe all functions, processes, and specifications for data collection, cleaning, and validation. The eCRFs will include programmable edits to obtain immediate feedback if data are missing, out of range, illogical or potentially erroneous. Concurrent manual data review will be performed based on parameters dictated by the plan. Ad hoc queries will be generated within the EDC system and followed-up for resolution.

Data collection standards will be maintained, and processes and procedures utilized to repeatedly ensure that the data are as clean and accurate as possible when presented for analysis. Data quality will be enhanced through a series of programmed data quality checks that automatically detect out of range or anomalous data.

9.6.1. Case report forms (CRFs)/Data collection tools (DCTs)/Electronic data record

As used in this protocol, the term CRF should be understood to refer to an electronic data record.

A CRF is required and should be completed for each included patient. The completed original CRFs are the sole property of Pfizer and should not be made available in any form to third parties, except for authorized representatives of Pfizer or appropriate regulatory authorities, without written permission from Pfizer. The investigator shall ensure that the CRFs are securely stored at the study site in encrypted electronic form and will be password protected or secured in a locked room to prevent access by unauthorized third parties.

The investigator has ultimate responsibility for the collection and reporting of all clinical, safety, and laboratory data entered on the CRFs and any other data collection forms (source documents) and ensuring that they are accurate, authentic/original, attributable, complete, consistent, legible, timely (contemporaneous), enduring, and available when required. The CRFs must be signed by the investigator or by an authorized staff member to attest that the data contained on the CRFs are true. Any corrections to entries made in the CRFs or source documents must be dated, initialed, and explained (if necessary) and should not obscure the original entry.

The source documents are the hospital or the physician's chart. In these cases, data collected on the CRFs must match those charts.

9.6.2. Record retention

To enable evaluations and/or inspections/audits from regulatory authorities or Pfizer, the investigator agrees to keep records, including the identity of all participating patients (sufficient information to link records, e.g., CRFs and hospital records), all original signed informed consent documents, copies of all CRFs, safety reporting forms, source documents, detailed records of treatment disposition, and adequate documentation of relevant correspondence (e.g., letters, meeting minutes, and telephone call reports). The records should be retained by the investigator according to local regulations or as specified in the clinical study agreement (CSA), whichever is longer. The investigator must ensure that the records continue to be stored securely for so long as they are retained.

If the investigator becomes unable for any reason to continue to retain study records for the required period (e.g., retirement, relocation), Pfizer should be prospectively notified. The study records must be transferred to a designee acceptable to Pfizer, such as another investigator, another institution, or to an independent third party arranged by Pfizer.

Study records must be kept for a minimum of 15 years after completion or discontinuation of the study, unless CRO and Pfizer have expressly agreed to a different period of retention via a separate written agreement. Record must be retained for longer than 15 years or as required by applicable local regulations.

The investigator must obtain Pfizer's written permission before disposing of any records, even if retention requirements have been met.

9.7. Data analysis

Detailed methodology for summary and statistical analyses of data collected in this study will be documented in a statistical analysis plan (SAP), which will be dated, filed and maintained by the sponsor. The SAP may modify the plans outlined in the protocol; any major modifications of primary endpoint definitions or their analyses would be reflected in a protocol amendment.

This study is descriptive in nature and no formal hypothesis testing will be conducted. Continuous variables will be summarized using n, mean, median, minimum, maximum, standard deviation (SD), and 25th and 75th percentiles, and in addition, 95% CI will be provided for effectiveness variables. Categorical variables will be summarized using number and percentages of each category. For continuous and categorical variables, missing data will not be imputed and will be reported as frequency and percentage. Missing data will not be included in the summary statistics. For time-to-event variables (such as time to alleviation of all targeted COVID-19 signs and symptoms), Kaplan Meier (K-M) plots will be generated, and median time will be estimated along with the corresponding 95% CI.

9.7.1. Analysis sets

- Full Analysis Set (FAS):

The FAS will include all patients who meet the inclusion criteria and do not meet the exclusion criteria described in section 9.2.

- Safety Analysis Set (SAS):

The SAS will include all patients from FAS.

- Effectiveness Analysis Set 1 (EAS1):

The EAS1 will include all patients from FAS who had at least one of the effectiveness variables collected and had the latest positive SARS-CoV-2 test result within 5 days prior to administration initiation.

- Effectiveness Analysis Set (EAS):

The EAS is a subset of EAS1 and will include patients who had mild or moderate COVID-19 illness at baseline and had at least one risk factor (defined in section 9.3.1) for progression to severe COVID-19 at baseline.

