COVID-19 severity	Secondary endpoint (effectiveness)	HIS	The first occurrence of severe or critical COVID-19 illness after initiation of nirmatrelvir/ritonavir treatment during observation period, and the date of this first occurrence will be abstracted. ²⁵ COVID-19 severity will be categorized into four levels. Apart from categories of severity level, names of the severity scale used and the relevant parameters used for severity assessment will also be

Table 1. List of variables and operational definitions

Variable	Role	Data source(s)	Operational definition
			abstracted from medical records. See section 9.3.2 COVID-19 Severity for categorization and parameters.
Death	Secondary endpoint (effectiveness)	HIS	Information on cause of death and the date of death will be abstracted.
Time to alleviation of all targeted COVID-19 signs and symptoms	Secondary endpoint (effectiveness)	HIS	Information on alleviation (yes/no) and severity level (if available, including absent, mild, moderate, and severe ²⁰) of each targeted sign/symptom of COVID-19 by date during the observation period will be abstracted from medical records. For a list of targeted signs and symptoms of COVID-19, see section 9.3.3 Signs/symptoms of COVID-19. For the definition of alleviation and the calculation of the time to alleviation, see section 9.3.7. Time to alleviation of all targeted COVID-19 signs and symptoms
Time to two consecutive negative SARS-CoV-2 test results / CT \geq 35	Secondary endpoint (effectiveness)	HIS/LIS	Medical records of dates, time and results of SARS-CoV-2 tests (positive/negative and CT values) after index date will be abstracted. See section 9.3.8 for calculating the time to two consecutive negative SARS-CoV-2 test results / CT \geq 35
Date of admission			As recorded in medical record.
Date of discharge from hospital			As recorded in medical record.

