9.5. Study size

There is no formal hypothesis testing for this study. This study is planned to include approximately 1000 individuals who initiated nirmatrelvir/ritonavir between 11 February 2022 and 31 August 2022. The primary objective of the study is to describe real-world safety of nirmatrelvir/ritonavir, and one of the primary safety endpoint is the proportion of patients experiencing AEs with explicit attribution to nirmatrelvir/ritonavir.

With a sample size of 1000, there will be a probability of >99.9% to observe an AE related to nirmatrelvir/ritonavir with a low incidence rate of 1% in at least one patient, and a probability of 95.0% to observe an AE related to nirmatrelvir/ritonavir with an even lower incidence rate of 0.3%²⁹ in at least one patient.

Table 4. Probabilities to observe an AE of different incidence rates

	Incidence rates		
Sample Size	1%	0.5%	0.3%
1000	> 99.9%	99.3%	95.0%

Note: The sample size and power is calculated based on the exact probabilities of the Binomial distribution, the probability of observing at least one event in n observations = $1 - (1-p)^n$.

For the effectiveness endpoint of proportion of patients with two consecutive negative SARS-CoV-2 test results, assuming that 20%³⁰ of patients will have negative SARS-CoV-2 test results from two consecutive respiratory specimens collected in two different calendar days, and 80% and 50% patients will be evaluable with at least one of the effectiveness endpoints data collected and in addition having at least one risk factor, samples of 800 and 500 individuals will provide a 95% CI with a half width of 2.77% and 3.50%, respectively.

Table 5. Precision for evaluating effectiveness for different numbers of evaluable patients

Scenarios	Evaluable patients	Half width of CI *
Included patients who had mild or moderate COVID-19 illness and had at least one risk factor at baseline for progression to severe COVID-19	500	3.50%
Included patients who had at least one of the effectiveness variables collected.	800	2.77%

*Note: The half width confidence interval is calculated according to the formula $z * \sqrt{p * (1 - p) / n}$, where $z = 1.96$ for a confidence level (α) of 95%, p = proportion, n = #of evaluable patients.

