9.7.3.2. Analysis of effectiveness endpoints

The analyses of effectiveness endpoints will be based on EAS1 and EAS, and the following will be presented:

Proportion of patients with COVID-19 disease severity (described in section 9.3.2) progressed or death from any cause and corresponding 95% CI will be summarized.

Time to alleviation of all targeted COVID-19 signs and symptoms (described in section 9.3.7) will be summarized by K-M plots with the median time and corresponding 95% CI.

Number and percentage of patients with two consecutive negative SARS-CoV-2 test results / CT \geq 35 (specimens collected in two different calendar days) and corresponding 95% CI will be summarized for the patients with at least two SARS-CoV-2 tests after treatment initiation.

Time to the first negative SARS-CoV-2 test result / CT \geq 35 from two consecutive negative SARS-CoV-2 test results / CT \geq 35 (specimens collected in two different calendar days) among patients with at least two SARS-CoV-2 tests (described in section 9.3.8) will be summarized and plotted in a K-M curve with the median time and corresponding 95% CI.

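### The EAS1 entry clause rests on post-dose data and can remove only event-free patients, so the progression-or-death proportion can be biased upward, by a factor of 1.00 to at most 1.25

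*Protocol*

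**What the plan says.** Section 9.7.1 of the protocol (repeated in the abstract) sets two conditions for EAS1:

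- a post-dose data condition: "The EAS1 will include all patients from FAS who had at least one of the effectiveness variables collected";
- a pre-dose condition: the patient "had the latest positive SARS-CoV-2 test result within 5 days prior to administration initiation".

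EAS is the part of EAS1 with mild or moderate illness and at least one risk factor at baseline. Section 9.7.3.2 then states: "The analyses of effectiveness endpoints will be based on EAS1 and EAS". The first endpoint listed there is the proportion who progressed or died, with a 95% CI.

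Table 1 in section 9.3 describes the data behind that endpoint. For severity, the item is "The first occurrence of severe or critical COVID-19 illness after initiation of nirmatrelvir/ritonavir treatment during observation period", with its date. The same row adds that "COVID-19 severity will be categorized into four levels" and that the scale and the assessment parameters are abstracted too. For death: "Information on cause of death and the date of death will be abstracted". The table has no item for survival without progression.

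Section 9.5 assumes that "80% and 50% patients will be evaluable with at least one of the effectiveness endpoints data collected", with a risk-factor condition added in the same sentence. Table 5 labels its row of 800 patients as those with at least one effectiveness variable available; that row does not mention the 5-day test rule. Section 9.7 says that missing data are neither imputed nor included in summaries.

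**The concern.** A denominator for a risk should be fixed by what is known at the start of treatment. Here it depends partly on what was charted afterwards, and for this endpoint the charting is linked to the outcome. A progression or a death creates the record that admits the patient. An uneventful stay creates no such record, so that patient needs some other post-dose entry to be counted.

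If some event-free patients have no such entry, they leave the denominator while no recorded event leaves the numerator. The proportion then comes out too high, and its CI is centred on the wrong value. The effect would be larger at sites with sparse charting or little follow-up testing. The protocol does not define when a variable counts as available, so two analysts could build different denominators for the same endpoint.

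**Working it through.** **The plan's own figures.** Section 9.5 uses half width = 1.96 × √(p(1−p)/n) with p = 0.20.

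- n = 800: 1.96 × √(0.16/800) = 2.77%. Stated: 2.77%.
- n = 500: 1.96 × √(0.16/500) = 3.51%. Stated: 3.50%, a rounding difference.

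These figures concern the viral endpoint. The protocol gives no assumed rate for progression or death.

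**Who can be removed.** Take the patients who already meet the pre-dose criteria of the set.

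| Patient | Severe/critical or death item in Table 1 | Other routes into the set | Can the clause exclude the patient? |
|---|---|---|---|
| Recorded progression or death | Present | Not needed | No |
| No recorded event | Absent | Symptom data, post-index tests, other severity data | Yes, if all are absent |

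The clause acts only on the second row, so its direction is fixed.

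**Size.** Let p be the true risk among patients who meet the pre-dose criteria, and q the share of them that the clause keeps. If all losses are event-free, reported risk = p/q and the inflation factor is 1/q:

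- q = 1.00: factor 1.00
- q = 0.95: 1/0.95 = 1.05
- q = 0.90: 1/0.90 = 1.11
- q = 0.80 (the section 9.5 planning figure): 1/0.80 = 1.25

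**Illustrations at q = 0.80.** The rates are assumptions. Each line starts from 1000 patients who meet the pre-dose criteria and keeps 800.

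| Assumed true risk | Events | Reported risk | Excess (points) | 95% CI half width, n = 800 (points) |
|---|---|---|---|---|
| 1% | 10 | 10/800 = 1.25% | 0.25 | 0.77 |
| 3% | 30 | 30/800 = 3.75% | 0.75 | 1.32 |
| 5% | 50 | 50/800 = 6.25% | 1.25 | 1.68 |
| 10% | 100 | 100/800 = 12.5% | 2.50 | 2.29 |

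The half width is 1.96 × √(r(1−r)/800), with r the reported risk. At this upper bound the excess is smaller than the half width at 1% to 5% and slightly larger at 10%. At q = 0.95 and a true 5%, the reported figure would be 50/950 = 5.26%, an excess of 0.26 points.

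**The case against.** The strongest case against is that the clause may exclude almost nobody.

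- Every patient is a symptomatic inpatient (section 9.2). Section 9.3.7 evaluates targeted symptoms seen at baseline or later and gives a censored time to anyone without an alleviation date. On that reading, most event-free patients have an effectiveness value even if alleviation was never charted. Those at risk of exclusion would be patients with no targeted symptom (section 9.3.3 leaves fatigue and objective fever off the targeted list), no post-index test and no severity entry.
- The severity row covers four levels, so a mild or moderate entry after dosing could also satisfy the clause.
- The 80% is a round planning scenario for the precision of the viral endpoint. Its sentence mixes data availability with a risk-factor condition.
- Progression or death is one of four secondary effectiveness endpoints, which the protocol does not rank, in a descriptive study.

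All of this stands, and it is why the factor is a range that starts at 1.00. It does not remove the point. The protocol itself fixes the set and assigns this endpoint to it, so the structure is not left to the SAP. If nearly everyone qualifies, the clause serves no purpose for this endpoint.

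Three stronger readings may tempt a reader, and the documents do not support them:

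- That every patient who progresses is counted. The 5-day test rule applies to them too, as do the baseline criteria for EAS.
- That the proportion is certainly overstated, by 25%. That is the upper bound, reached only under the two conditions in the working.
- That EAS is inflated by 1/0.50 = 2. The row of 500 in Table 5 already reflects baseline severity and risk factors, so most of that reduction need not come from absent data.

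**Conclusion.** The point holds as a conditional one. For progression or death, EAS1 and EAS are defined partly by post-dose data that a recorded event supplies automatically. Among patients who meet the pre-dose criteria, the clause can remove only those without an event, so it can bias the proportion upward and never downward.

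The factor lies between 1.00 and 1.25. The upper end assumes that the 80% planning figure describes the effect of this clause and that all losses are event-free. At an assumed true 5%, the reported proportion would be 5.0% to 6.25%. The actual value could be close to the lower end, because many event-free inpatients will have symptom or test data. The point merits a change because the direction is known, the wording is open to two readings, and the correction is cheap.

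**What to change.** In section 9.7.1 and the abstract, for progression or death only:

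1. Define EAS1 as FAS patients who meet the 5-day positive-test rule. Define EAS as those among them with mild or moderate illness and at least one risk factor at baseline. Drop the data-availability clause.
2. Count a patient with no severe, critical or death record through the end of observation as event-free. State this as a rule for ascertaining the event, so that it does not conflict with the no-imputation rule in section 9.7.
3. Report how many patients have no post-dose severity record, and repeat the analysis without them.
4. Keep data-availability conditions for the symptom and viral-test endpoints. The viral endpoints already require at least two tests after initiation.

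The cost is a few sentences. No new data are needed: observation ends at the earliest of discharge, death and 28 days from the final dose, and discharge date, severity items and death are already in Table 1.

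There are two downsides. Absence of a record is read as no event, which could understate progression where charting is sparse. The sensitivity analysis errs in the opposite direction, so the pair brackets the answer if patients without a severity record have no higher risk than those with one. The denominators may also differ from the 800 and 500 in Table 5.

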9.2. Setting

Study population will consist of patients who initiated treatment with nirmatrelvir/ritonavir between 11 February 2022 and 31 August 2022 during hospitalization. Approximately 1000 patients are planned to be included in the study. Eligible patients must meet the following inclusion criteria and none of the exclusion criteria:

Inclusion criteria

- Chinese patients aged \geq 18 years on index date
- Patients initiated and took at least one dose of nirmatrelvir/ritonavir between 11 February 2022 and 31 August 2022 during hospitalization
- Patients had documented confirmed symptomatic COVID-19 with positive SARS-CoV-2 test in any specimen collected prior to or at initiation of nirmatrelvir/ritonavir
- Evidence of a personally signed and dated ICD indicating that the patient (or a legally acceptable representative) has been informed of all pertinent aspects of the study if requested by study sites.

Exclusion criteria

- Patients participated in any interventional COVID-19 trials during the study period.

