Duration since first COVID-19 symptom/sign	Baseline clinical characteristics / subgroup identifier	HIS	It is defined as the duration between onset date of the first COVID-19 related symptom/sign and the index date. The equation will be: (Index date) – (Onset date of the first COVID-19 symptom/sign abstracted from the medical records during baseline period) + 1. See section 9.3.3 for a list of COVID-19 signs/symptoms in detail.
Presence and severity of any COVID-19 symptoms/signs at baseline	Baseline clinical characteristics	HIS	Severity level of each COVID-19 symptom/sign will be abstracted from medical records. Categories of severity levels of each COVID-19 symptom/sign will be absent, mild, moderate and severe. ²⁰ The assessment on or closest to the index date will be used.
Duration between the first positive SARS-CoV-2 test and index date	Baseline clinical characteristics	HIS/LIS	The following information about the SARS-CoV-2 tests will be abstracted from medical

Table 1. List of variables and operational definitions

Variable	Role	Data source(s)	Operational definition
SARS-CoV-2 test status at baseline	Baseline clinical characteristics	HIS/LIS	
records if available: test type (i.e., NAT [nucleic acid test] or antigen test), sampling site, sampling date and time, test result date and time, test result (positive vs. negative, and CT value if available).
 
Duration = (Index date) – (Sampling date of the first positive SAR-CoV-2 test abstracted from the baseline period medical records) +1
 
Baseline test status will be the latest assessment prior to or on the index date.

Renal laboratory results at baseline	Baseline clinical characteristics / subgroup identifier	HIS/LIS	
Renal laboratory results are measured by the estimated glomerular filtration rate (eGFR; mL/min/1.73m²). The serum creatinine and the eGRF (if available) will be collected as recorded in medical records.
 
CKD-EPI Equation:²³ $eGFR = 141 \times \min(Scr/\kappa, 1)^\alpha \times \max(Scr/\kappa, 1)^{-1.209} \times 0.993^{Age} \times 1.018 \text{ [if female]} \times 1.159 \text{ [if Black]}$
 
where: Scr is serum creatinine in mg/dL, κ is 0.7 for females and 0.9 for males, α is -0.329 for females and -0.411 for males, min indicates the minimum of Scr/κ or 1, and max indicates the maximum of Scr/κ or 1.
 
Patients will be categorized into four groups:
 
 eGFR ≥ 90 mL/min/1.73m² eGFR ≥ 60 and < 90 mL/min/1.73m²

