9.3.7. Time to alleviation of all targeted COVID-19 signs and symptoms

The targeted signs and symptoms of COVID-19 (described in section 9.3.3) will be used for the analysis of time to alleviation calculation. For a patient, the targeted signs and symptoms recorded in either baseline or observation period will be evaluated.

The First Alleviation Date for a targeted sign/symptom is the date when alleviation is firstly recorded in medical records during the observation period

Event Date = The last date of (The First Alleviation Dates for ALL targeted signs/symptoms to be evaluated)

The time to alleviation of all targeted COVID-19 signs and symptoms is defined as:

- For a patient with the Event Date, it will be calculated as (Event Date) – (Index Date) +1.
- For a patient without the Event Date, it will be calculated as (End of Observation Date) – (Index Date) +1 and be considered as a censoring time. ^{7 12}

9.3.8. Time to two consecutive negative SARS-CoV-2 test results / CT ≥ 35

For patients with at least two SARS-CoV-2 tests (specimens collected in two different calendar days) after treatment initiation during observation period, the first day of a negative SARS-CoV-2 test / CT ≥ 35 from two consecutive negative results is considered as an Event Date.

The time to event of two consecutive negative SARS-CoV-2 test results / CT ≥ 35 in this study is defined as:

- For a patient with the Event Date, it will be calculated using (Event Date) – (Index Date) +1.
- For a patient without the Event Date, it will be calculated as (End of Observation Date) – (Index date) + 1 and be considered as a censoring time.

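### EAS1 dates the last positive test but does not require patients to be positive by the endpoint's own rule at the first dose, so some can be counted as viral conversions without any change in status

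*Protocol*

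**What the plan says.** EAS1 (section 9.7.1, repeated in the abstract) takes patients from the FAS with at least one effectiveness variable who "had the latest positive SARS-CoV-2 test result within 5 days prior to administration initiation". The narrower set inherits this condition: "The EAS is a subset of EAS1 and will include patients who had mild or moderate COVID-19 illness at baseline", and it adds only a risk factor.

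The inclusion criterion in section 9.2 asks for a "positive SARS-CoV-2 test in any specimen collected prior to or at initiation of nirmatrelvir/ritonavir". It sets no CT limit and no condition on the last test.

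Table 1 (section 9.3) abstracts the "test result (positive vs. negative, and CT value if available", so the reported result and the CT are separate items. It also states: "Baseline test status will be the latest assessment prior to or on the index date". That variable is listed as a baseline characteristic only. It defines no analysis set and is not among the subgroups in section 9.7.4.

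The two viral endpoints (sections 9.1.2, 9.3.8 and 9.7.3.2) are analysed in EAS1 and EAS. Section 9.3.8 opens its rule with "For patients with at least two SARS-CoV-2 tests (specimens collected in two different calendar days) after treatment initiation during observation period". The event is the first day of two consecutive results that are negative or have CT of 35 or more, and time runs from the index date.

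**The concern.** A conversion endpoint describes a change from positive to negative, so patients should be positive at the start by the rule that later decides they are negative. The protocol does not secure this, for two reasons.

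- **Last test.** A patient positive four days before the first dose and negative one day before it satisfies the literal wording, because the most recent positive lies within 5 days.
- **Threshold.** A reported positive with CT 36 qualifies for entry. The same value after the first dose counts towards conversion.

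Neither the endpoint's denominator nor any planned subgroup separates these patients. The study has a single arm, so no comparator carries the same bias. At stake are two secondary endpoints: the conversion proportion, which would be too high, and the Kaplan-Meier curve with its median, which would move earlier.

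**Working it through.** **1. The plan's own figure.** Section 9.5 assumes p = 20% and uses a half-width of 1.96 × √(p(1−p)/n).

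- n = 800: 1.96 × √(0.16/800) = 2.77% (stated 2.77%)
- n = 500: 1.96 × √(0.16/500) = 3.51% (stated 3.50%, a rounding difference)

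**2. Who can enter.**

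| Last result before first dose | Enters EAS1? | Same result under the 9.3.8 rule |
|---|---|---|
| Positive, CT below 35 | Yes | Not negative |
| Reported positive, CT 35 or more | Yes, on either reading | Counts as negative |
| Negative, after a positive within 5 days | Yes, on the literal reading | Counts as negative |

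The last two rows are the problem group.

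**3. Size of the bias.** Two inputs are assumptions, because the protocol gives neither:

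- q: the share of analysed patients already negative or at CT of 35 or more at the last test before the first dose
- c: the chance that such a patient has two consecutive qualifying results after the index date

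Reported proportion = q × c + (1 − q) × p, so the shift is q × (c − p). It is upward whenever c exceeds p.

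With p = 20%:

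| q | c = 0.8 | c = 1.0 | Share of counted events from the problem group |
|---|---|---|---|
| 5% | 0.04 + 0.19 = 23% | 0.05 + 0.19 = 24% | 17-21% |
| 10% | 0.08 + 0.18 = 26% | 0.10 + 0.18 = 28% | 31-36% |
| 20% | 0.16 + 0.16 = 32% | 0.20 + 0.16 = 36% | 50-56% |

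At q = 5% the shift is 3 to 4 points. The lower value passes 2.77% but not 3.50%; the upper value passes both. At q = 10% the shift of 6 to 8 points passes both. With c = 1, the shift equals the half-width at q = 0.0277/0.8 = 3.5% (n = 800) and q = 0.0351/0.8 = 4.4% (n = 500).

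**4. Sensitivity to p.** Take p = 60%, an illustrative value that is not in the protocol, with q = 10%.

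- c = 0.8: 0.08 + 0.54 = 62%, a shift of 2 points
- c = 1.0: 0.10 + 0.54 = 64%, a shift of 4 points
- Half-widths at p = 60%: 1.96 × √(0.24/800) = 3.39% and 1.96 × √(0.24/500) = 4.29%

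The shift passes only the n = 800 half-width, and only with c = 1.

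**5. Time to conversion.** A patient who is already negative and stays so has the event at the first test after the index date. This adds early events and moves the curve, and the median if it is reached, to the left. The protocol gives no input from which to compute that shift.

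**The case against.** The strongest reply is that the EAS1 wording is ambiguous rather than wrong: it can be taken to mean that the latest test was positive and fell within 5 days. Table 1's definition of baseline status from the latest assessment fits that reading. If so, the case of a later negative test disappears. This part stands, but it does not settle the matter. The CT mismatch remains, because nothing requires a baseline positive to have CT below 35.

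A reader might also infer that these patients already meet the endpoint at entry and are certain to be counted. The documents do not support that. The endpoint needs two consecutive qualifying results on different days after the first dose. One negative or one CT of 36 beforehand is not that criterion, and a later positive can break the pair. Such patients can be counted; they are not bound to be. Setting c = 1 is therefore an upper case.

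A reader might further see errors in three other places: antigen and nucleic acid tests are both abstracted; section 9.5 speaks of "negative SARS-CoV-2 test results from two consecutive respiratory specimens collected in two different calendar days" while section 9.3.8 names no specimen type; and the index day is worded differently in sections 9.2 and 9.7.1. The protocol does not say that test types or sampling sites are pooled. These are derivation details that an SAP commonly settles, and they are not part of this point.

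Finally, the study is descriptive, without a hypothesis test or comparator, so no treatment effect is distorted. That limits the severity. It does not remove the bias in the two proportions and times that will be reported.

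**Conclusion.** The point holds for the two viral endpoints. The entry rule and the endpoint rule are inconsistent on CT under any reading, and on the last test under the literal one. The bias raises the conversion proportion and shortens the time to conversion.

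With p = 20% and c between 0.8 and 1.0, the reported proportion would be 23-24% at q = 5% and 26-28% at q = 10%. Both q and c are assumptions, so the protocol shows that the bias is possible and in which direction it runs, but not how large it will be. At a higher true proportion it may lie within the half-width.

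This should be fixed, but it does not threaten the study: the endpoints are secondary, and the primary safety endpoints and the other two effectiveness endpoints do not depend on it.

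**What to change.** For the two viral endpoints only, add to sections 9.7.1 and 9.3.8 that the latest test on or before the index date, and within 5 days of it, must be positive by the endpoint's own rule: CT below 35 where a CT is available, reported positive otherwise. Report patients who do not meet this separately. Keep the present EAS1 for the symptom and progression endpoints.

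The data are already abstracted under Table 1 (result, CT where available, sampling date and time), so the change is one of wording and derivation.

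The cost is a smaller viral analysis. At q = 10%, n falls from 800 to 720 and from 500 to 450, and the half-widths at p = 20% become 1.96 × √(0.16/720) = 2.92% and 1.96 × √(0.16/450) = 3.70%. Positives without a CT remain a residual leak, because some may truly be at 35 or more; their number should be reported.
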